3 INVESTIGATIONAL PLAN

3.1 General Schema of Study Design

The project will be conducted as part of a K23 career development award with three aims. Each aim represents a sub-study of the overarching study to achieve the overall goal. Aims 1 and 2 will occur sequentially and each should take approximately a year to complete. The results of Aim 1 and 2 will go to inform the randomized control trial (RCT) in Aim 3. However, Aim 3 enrollment can occur even if there is no enrollment in Aim 2. Aim 3 will occur over a 12-18-month period.

Aim 1: Observational, qualitative, cross-sectional study (n~50). Youth with complete one of five focus groups (~5-8 youth per group) or an in-depth interview to identify barriers and facilitators to HIV/STI prevention behavior to be addressed in the intervention and determine preferences for intervention format and delivery strategy. Participants will also complete a brief CASI at the time of study enrollment after informed consent. At the end of each focus group and in-depth interview, we will remind participants of where they can access sexual health and preventative care services and we will share the clinics' contact information. It is of note that Aim 1 focus groups might not occur if any conditions prohibit the gathering of focus groups within the primary care setting.

Aim 2: Observational, mixed methods using chart stimulated recall (CSR), in-depth interviews, and quantitative measurement of acceptability, feasibility and appropriateness of the PrEP-inclusive coaching intervention in pediatric primary care. Participants will complete a single study visit with completion of CSR, semi-structured audio-recorded interviews, and a computer assisted survey instrument (CASI) delivered on a secure tablet or laptop with acceptability, feasibility, and appropriateness measures.

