Aim 3: We will conduct 1) an iterative pilot phase followed by 2) a small RCT assessing intervention effect on the intermediate target of prevention self-efficacy. Pilot testing will occur over a 3-month period to prime intervention for implementation, with the aim of recruiting n=10 pilot participants. Pilot phase participants will follow the same study procedure timeline as participants randomized to the coaching intervention arm of the RCT, excluding the 6-month follow-up visit. Pilot participants will not be followed in the RCT or contribute outcome data. At the end of every health coaching visit (the baseline, 1-week, 1-month and 3-month visits), pilot phase participants will complete a brief feedback interview to ensure face validity and identify areas needing refinement. Feedback will be incorporated into the study design, with amendments submitted to the IRB as needed. The RCT will randomize youth with recent STI 1:1 to the coaching intervention vs a standard of care (SOC) control. If difficulty retaining coaching participants during the RCT generates a disparity in evaluable participants per arm, the RCT's randomization scheme will be changed to 2:1, intervention vs SOC, to balance numbers of evaluable participants per arm. Both arms (intervention and SOC) will have data collection visits at the baseline, the 3-month, and the 6-month-follow-up time points. In addition, the intervention group will have health coaching sessions at baseline, 1 week, 1 month and 3 months. At the end of the 3-month health coaching visit, a sample of RCT phase participants assigned to the intervention arm will complete a brief feedback interview to ensure face validity and identify areas needing refinement for future studies.

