3.2 Allocation to Treatment Groups and Blinding

Aim 1: N/A

Aim 2: N/A

Aim 3: Non-stratified 1:1 randomization will occur at baseline using the REDCap randomization tool based on randomization tables. The study team will not be able to change study groups for participants once randomization has taken place. The randomization will not be blinded to the participants or the study team because of the nature of the intervention.

As mentioned in Section 3, if difficulty retaining coaching participants during the RCT generates a disparity in evaluable participants per arm, the RCT's randomization scheme will be changed to 2:1, intervention vs SOC, to balance numbers of evaluable participants per arm.

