5.2 Efficacy Evaluations

These are the measures that will be used to assess the efficacy of the study intervention

Aim 1: N/A

Aim 2: N/A

Aim 3: The primary efficacy outcome is the difference in change in self-efficacy between baseline and six-month visits for the intervention group versus control, as measured by the modified Generalized Self-Efficacy Scale.

5.2.1 Diagnostic Tests, Scales, Measures, etc.

See the list of CASIs in section 5.1.3.1 above.

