6.3.2 Analysis

Aim 1: We will conduct a deductive qualitative analysis of focus group transcripts and in-depth interview transcripts with our theoretical model guiding the coding process. Codes related to model constructs will be assigned to interview segments to organize the data, using the software NVivo, with two study team members separately reviewing the first 10 transcripts line by line, assigning codes as concepts become apparent. We will compare text segments to those that have been previously assigned the same code, and to segments coded separately by each analyst, to decide whether they reflect the same concept. We will use this process to generate a coding scheme, then apply it to all transcripts. Once coding is complete, we will review the data to document emerging themes-general insights gleaned from the entirety of the data- which may inform intervention content.

Aim 2: Survey data will be summarized via descriptive statistics. We will set a >80% threshold for high acceptability, feasibility and appropriateness. The interview coding process will parallel that described in Aim 1. We will use an integrated deductive and inductive coding approach. Transcripts will be reviewed using deductive methodology, where CFIR determinants will be used as the coding framework. After completion, the transcripts will be re-reviewed using inductive methodology where codes identifying novel barriers and facilitators of implementation that do not map onto the CFIR will be identified and used to develop a coding framework that is then applied to all transcripts. We will integrate the qualitative and quantitative data by merging findings through a comparative coding analysis. The AIM and FIM scores will be dichotomized (completely disagree/disagree vs completely agree/agree). We will compare the distribution of content themes between providers with high vs low acceptability and, separately, high vs low feasibility ratings. Data will then be used as a starting point in which to build an optimized PrEP-inclusive coaching implementation strategy to be tested in the subsequent RCT.

Aim 3: The primary analysis will be based on an intention to treat approach and will include all subjects randomized at Visit 1.

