The primary outcome for the RCT is the change in prevention self-efficacy between intervention and control conditions between the baseline and six-month (final) visits. We will compare the exposure variable of treatment group with the outcome variable of continuous score on the modified Generalized Self-Efficacy Scale at baseline, intermediate (e.g. three month), and six-month visits using mixed effects logistic regression models with a random intercept for patient and a random slope for time. In exploratory analyses, to determine if the mental health predictors impact the self-efficacy outcome, we will create separate mixed effects regression models to compare self-efficacy score for those with and without mood ratings consistent with depression on the PSC-17, high trauma (Adverse Childhood Experiences Scale score >4 vs not), and substance abuse (CRAFFT score >4) adjusting for treatment group and demographic characteristics including sex. In order to assess the impact of STI timing on the primary outcome of prevention self-efficacy, we will use linear regression models and days between STI diagnosis and the first coaching visit in the intervention group, adjusting for demographic covariates including sex and sexual orientation. Finally, we will assess if coaching may have a significant effect on other domains in the self-efficacy pathway of our model, by repeating the primary analysis above with scores for the Patient Activation Measure [PAM], and Confidence in Safer Sex Scale.

There will be no adjustment of p value for multiple comparisons given the exploratory nature of these analyses.

Secondary outcome analyses:

- Referral feasibility: Calculated as the number of potential participants referred to study staff over the number of patients with bacterial STI at the clinics during the study period. This denominator will be identified using the CHOP STI dataset.
- Recruitment feasibility: Calculated as the number of patients enrolled over the number of patients referred.

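### No allocation-period term is planned for the conditional 1:1 to 2:1 switch, so part of any drift in the 0-6 month GSES change would enter the treatment effect: small, and cheap to prevent

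*Combined protocol and SAP*

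**What the plan says.** Randomization in Aim 3 starts as simple, non-stratified 1:1 (sections 3.2 and 9.1.1). Section 3.1 sets the condition for a change: "If difficulty retaining coaching participants during the RCT generates a disparity in evaluable participants per arm". Sections 3.2 and 9.1.1 repeat that the "randomization scheme will be changed to 2:1, intervention vs SOC, to balance numbers of evaluable participants per arm". No threshold or date is given, and evaluable is not defined.

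The endpoint in section 5.2 is the "difference in change in self-efficacy between baseline and six-month visits for the intervention group versus control". The intention-to-treat analysis in section 6.3.2 "will include all subjects randomized at Visit 1", so both allocation periods are pooled. The primary comparison uses the "outcome variable of continuous score on the modified Generalized Self-Efficacy Scale" at baseline, three and six months, "using mixed effects logistic regression models with a random intercept for patient and a random slope for time". The same model serves other scales by "repeating the primary analysis above with scores for the Patient Activation Measure" and the Confidence in Safer Sex Scale. None of these between-arm models includes allocation period, enrolment date or calendar time. The demographic covariates in 6.3.2 belong to the exploratory, STI-timing and retention models.

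**The concern.** Allocation is random within each period, but not with the same probability. Once the periods are pooled, arm is associated with enrolment date: the coaching arm holds proportionally more late enrollees. Anything that makes late enrollees change more, or less, than early ones in both arms then appears as a difference between arms.

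Two conditions are needed together: the switch happens, and the 0-6 month change drifts over enrolment. A drift in level that persists across visits does no harm, because the endpoint is a change and the shift cancels within each participant. The direction of any bias cannot be known in advance.

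The trial is unblinded and the trigger has no threshold. A period term added after results were seen would look like an analyst's choice; one written down beforehand would not.

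**Working it through.** **Inputs.** From the documents: N = 150, 1:1 then 2:1, two-sided alpha 0.05, and a target of 0.7-0.9 SD (section 6.4). Assumed, because the documents are silent: switch after k = 50, 75, 100 or 120 participants; drift D = 0.2, 0.3 or 0.5 SD of the change score; retention 70% coaching and 90% SOC. All figures use a linear model. Section 6.3.2 names a logistic one for a continuous score, which is a separate issue.

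**The plan's own figure.** The 0.7-0.9 SD serves only as a yardstick. With 67.5 per arm after 10% loss, the detectable difference is 2.80 × √(2(1−ρ)) × √(2/67.5). That is 0.68 SD at ρ = 0.01 and 0.57 SD at ρ = 0.3. The lower end of the stated range is therefore roughly reproduced and the upper end is not. This does not affect the present point.

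**Share of drift that enters the effect.** Expected coaching n = k/2 + 2(150−k)/3; SOC n = k/2 + (150−k)/3. For k = 75 these are 37.5 + 50 = 87.5 and 37.5 + 25 = 62.5. Late shares are 50/87.5 = 57.1% and 25/62.5 = 40.0%, a gap of 0.171. The gap multiplies a step at the switch date. For a linear drift the factor is half the gap, because the mean enrolment positions of the two periods are half the enrolment range apart. Retention that differs only by arm leaves the gap unchanged.

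| Switch after | Late, coaching | Late, SOC | Share, step | Share, linear | Information kept with period term |
|---|---|---|---|---|---|
| 50 | 72.7% | 57.1% | 0.156 | 0.078 | 0.974 |
| 75 | 57.1% | 40.0% | 0.171 | 0.086 | 0.971 |
| 100 | 40.0% | 25.0% | 0.150 | 0.075 | 0.975 |
| 120 | 25.0% | 14.3% | 0.107 | 0.054 | 0.982 |

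The last column is [k/4 + 2(150−k)/9] divided by (coaching n × SOC n / 150). For k = 75 this is 35.42/36.46 = 0.971, so the standard error rises by 1/√0.971 = 1.015.

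**Bias and type I error, k = 75.** Simulation of the change score (SD 1, no true effect, simple randomization, 40,000 runs per cell, Monte Carlo error about 0.1 point):

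| Drift (SD) | Step: bias | Step: type I error | Linear: bias | Linear: type I error |
|---|---|---|---|---|
| 0.2 | 0.034 | 5.4% | 0.017 | 5.0% |
| 0.3 | 0.051 | 5.9% | 0.026 | 5.2% |
| 0.5 | 0.086 | 7.4% | 0.043 | 5.7% |

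Hand check: SE = √(1/61.25 + 1/56.25) = 0.185. A 0.3 SD step gives 0.0514/0.185 = 0.28 standard errors and a rejection rate of 5.9%. A 0.5 SD step gives 0.46 and about 7.5%, slightly above the simulation because this SE omits the variance that the drift itself adds.

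For drift of 0.3 / 0.5 SD, a switch after 100 gives 5.6% / 6.7% (step) and 5.3% / 5.7% (linear). A switch after 120 gives 5.4% / 5.8% and 5.2% / 5.4%. With a period term, every cell is 4.8-5.2% and mean bias is within 0.003 SD of zero.

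**Which term works.** In a linear mixed model with visits at 0, 3 and 6 months, random intercept and slope, and complete data, the bias in arm × time per unit of step drift (k = 75) is 0.171 without a period term. It is still 0.171 with a period main effect alone, and 0.000 with period × time. For linear drift the values are 0.086, 0.086 and 0.000.

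**Room for drift and for a switch.** Section 3.1 states "Aim 3 will occur over a 12-18-month period". Subtracting about 3 months of pilot and 6 of follow-up (section 3.3.1) leaves 12 − 3 − 6 = 3 to 18 − 3 − 6 = 9 months of RCT enrolment. With even accrual over 9 months, the first three-month visits fall due at 150 × 3/9 = 50 enrolled and the first six-month visits at 150 × 6/9 = 100. With a 3-month window, enrolment ends as the first three-month visits fall due.

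**The case against.** The case against acting is about consequence. The harm needs a switch and a drift in the change score, and the documents suggest no cause for such drift: refinement of the intervention is placed in the pilot, whose participants contribute no outcome data. Nothing says a step would coincide with the switch. Under smooth drift of 0.2-0.3 SD, type I error stays at 5.0-5.3% for every switch point examined. The term is also not free once a switch has occurred. At k = 75 the root mean squared error with and without it is about 0.189 and 0.185 with no drift, and 0.1885 and 0.1870 with 0.3 SD linear drift. It clearly gains only for steps of 0.3 SD or more. Finally, the switch would be triggered by differential coaching dropout, which is a larger problem that a period term does not touch.

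All of this is fair and limits the weight of the point, but it does not remove the gap. The switch is a contingency that the plan itself sets out, drift cannot be ruled out in advance, and the loss of precision is slight. Analysing by the periods in which participants were actually randomized keeps the test valid whatever the drift.

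**Conclusion.** The point holds as a minor improvement. No allocation-period term is planned. If the ratio changes and the 0-6 month change drifts in both arms, at most about 17% of a step drift or 9% of a linear drift enters the treatment effect. For the assumed drifts of 0.2-0.5 SD at a half-way switch, the bias is 0.017-0.086 SD and type I error is about 5.0-7.4%. Against a 0.7-0.9 SD target, in a small RCT meant to inform a later fully powered trial (section 10), this would rarely change the conclusion. Drift size, switch point and retention are assumptions, and the calculations use a linear model. Without a switch or without drift there is no bias.

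**What to change.** Add to section 6.3.2 (Aim 3), before any switch: 'If the allocation ratio is changed, the date of the change will be recorded. Every between-arm model will include allocation period (randomized before or after the change) and, in the longitudinal models, its interaction with visit time.' The interaction is essential, because a period main effect alone leaves the bias in the longitudinal model untouched. Estimating the effect within each period and combining the two with precision weights is an alternative that amounts to the same under a common treatment effect.

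The cost is one sentence and one recorded date. If a switch occurs, the term gives up about 2-3% of information (2.6%, 2.9%, 2.5% and 1.8% for switches after 50, 75, 100 and 120), or at most about 1.5% in standard error. If no switch occurs, it costs nothing. Differential dropout from coaching needs its own treatment in the plan.

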3.3 Study Duration, Enrollment and Number of Sites

3.3.1 Duration of Study Participation

Aim 1: Study duration for Aim 1 will be two days, as the first day participants will complete the CASI at time of consent, and the second day (scheduled based on participant availability, they will complete the virtual or in-person focus group or in-depth interview).

Aim 2: Study duration for Aim 2 will be one day for completing all the activities.

Aim 3:

Pilot phase: We will use pilot testing over a projected 3-month period to ensure that intervention critical steps are primed for implementation. Over one month, we aim to recruit n=10 participants. Pilot phase participants will follow the same study procedure timeline as participants randomized to the coaching intervention arm of the RCT, excluding the 6-month follow-up visit, and will not be followed in the RCT or contribute outcome data. At the end of every health coaching visit (the baseline, 1-week, 1-month and 3-month visits), pilot phase participants will complete a brief feedback interview to ensure face validity and identify areas needing refinement. Following this phase, we will systematically review

feedback and adapt the study design and strategy as needed prior to the RCT, with amendments submitted to the IRB as needed for modifications to study design.

Intervention phase: Study duration for Aim 3 will consist of data collection and health coaching visits over a 6-month period (see Table 1: Schedule of Study Procedures for Aim 3 RCT), with the baseline visit as the study's start. Visit windows, as described in Table 1, show that the 1 week visit window is +7/-5 days, the 1 month visit window is + 30/- 14 days, the 3-month visit window is + 30/- 14 days, and 6-month visit window is +/- 30 days.

3.3.2 Total Number of Study Sites/Total Number of Subjects Projected

The study, including all three aims, will be conducted at investigative sites in the United States. For Aim 1, participants will be recruited from two clinics affiliated with the Children's Hospital of Philadelphia (CHOP) that house Title X adolescent family planning clinics, Karabots Care Network and Cobbs Creek Care Network, from the Adolescent Specialty Clinic, and by word-of-mouth referral from existing participants. For Aim 2, participants will be recruited from two clinics affiliated with the Children's Hospital of Philadelphia (CHOP) that house Title X adolescent family planning clinics, Karabots Care Network and Cobbs Creek Care Network. For Aim 3, participants will be recruited from Children's Hospital of Philadelphia (CHOP) primary care clinics.

Analysis and study coordination will occur at the Roberts Center for Pediatric Research of the Children's Hospital of Philadelphia.

Aim 1: Recruitment goal for Aim 1 is 50 participants, recruited in groups of 5-8 for virtual or in-person focus groups or in-depth interviews. Once this number is reached, recruitment will stop.

Aim 2: Recruitment goal for Aim 2 is 25 clinicians, clinic staff, and administrators are recruited from the primary care clinics. Once this number is reached, no more providers will be recruited.

Aim 3: Recruitment goal for the pilot phase is 10 participants. Recruitment goal for the RCT is 150 participants, 75 for each arm (with the chance of more participants in the RCT's intervention arm than control arm if there are changes to the randomization scheme).

3.4 Study Population

3.4.1 Inclusion Criteria

Aim 1

- 1) Males or females age 13 to 19 years.
- 2) History of ≥ 1 STI
- 3) Able to speak and understand written English

- 4) Able to access internet, a mobile device or computer, and video conferencing using a HIPAA compliant CHOP approved vendor. During the COVID-19 Pandemic, study procedures must be conducted remotely to protect participant safety; this is only applicable to Aim 1 and will not apply to the remainder of the study.

Aim 2

- 1) Clinical providers (physicians, certified nurse practitioners, physician assistants, and registered nurses) who provide clinic care to ≥ 1 adolescent patient diagnosed with an STI in the past year.
- 2) Able to speak and understand written English

Aim 3

- 1) Males or females aged 13 to 19 years.
- 2) Seeking STI-related testing, treatment, prevention counseling, or follow-up care
- 3) History of ≥ 1 STI in the 30 days prior to recruitment
- 4) Confirmed treatment for a laboratory-confirmed diagnosis of Trichomonas vaginalis (via microscopy or nucleic acid amplification test [NAAT]), Neisseria gonorrhoea (NAAT), Chlamydia trachomatis (NAAT), or Treponema pallidum (via new positive rapid plasmin reagent [RPR] assay) within the prior 30 days
- 5) Self-reported HIV negative status and/or HIV negative status as per medical record review
- 6) Able to speak and understand written English
- 7) If participating in remote visits, must be able to access internet, a mobile device or computer, and video conferencing using a HIPAA compliant CHOP approved vendor. If attending in-person visits, must be able to access a phone for scheduling in-person visits.

3.4.2 Exclusion Criteria

All aims

- 1) Unable to provide informed consent due to intoxication or severe psychological distress.

Subjects that do not meet all of the enrollment criteria may not be enrolled. Any violations of these criteria must be reported in accordance with IRB Policies and Procedures.

4 STUDY PROCEDURES

4.1 Screening/Baseline Visit

Aim 1

- Informed Consent
- Survey questionnaire
- Virtual or in-person focus group or in-depth interview: Given the sensitive nature of the topic, we recognize that some youth may not be comfortable in the group setting. At the time of informed consent, participants will have the ability to opt-out of the focus group and instead conduct an individual, audio or video recorded, in-depth interview. In addition, if participants who have opted for focus group participation are unable to attend the group at the scheduled time or no-show for the focus group, they will be offered the option of conducting an in-person, or if necessary, a telephone or video conferencing interview using a HIPAA compliant CHOP approved vendor.
- At the end of each focus group and in-depth interview, we will remind participants of where they can access sexual health and preventative care services and we will share the clinics' contact information.

Aim 2

- Informed consent
- Chart simulated recall
- In-depth interview
- CASIs measuring demographics acceptability, feasibility, and appropriateness of PrEP in pediatric care

Aim 3

- Informed Consent
- Randomization
- Computer assisted survey instruments (See Section 5.1.3.1)
- Health coaching
- Electronic medical record review

